3.2 Post Study Access to Therapy

At the end of the study, BMS will not continue to provide BMS supplied study drug to subjects/investigators unless BMS chooses to extend the study. The investigator should ensure that the subject receives appropriate standard of care to treat the condition under study.

3.3 Study Population

For entry into the study, the following criteria MUST be met prior to dosing on Day 1. No exceptions will be granted.

3.3.1 Inclusion Criteria

1. Signed Written Informed Consent

- a) Signed written informed consent must be obtained from the subjects in accordance with requirements of the study center's IRB/IEC prior to the initiation of any protocol-required procedures.

2. Target Population

- a) Healthy male and female subjects, including women of childbearing potential (WOCBP), as determined by no significant deviation from normal in history, physical examination, vital signs, ECGs, and clinical laboratory determinations.
- b) Must weigh between 60.0 to 100.0 kg, inclusive.
- c) Must have body mass index (BMI) of 18.0 to 30.0 kg/m², inclusive; BMI=weight (kg)/[height (m)]².
- d) Subject re-enrollment: This study permits, at the discretion of the investigator, the re-enrollment of a subject that has discontinued the study as a pre-treatment failure (ie, subject has not been randomized / has not been treated). If re-enrolled, the subject must be re-consented.

3. Age and Reproductive Status

- a) Males and females, ages 18 to 55 years, inclusive.
- b) WOCBP must have a negative serum or urine pregnancy test (minimum sensitivity 25 IU/L or equivalent units of human chorionic gonadotropin within 24 hours prior to the start of study drug).
- c) Women must not be breastfeeding.
- d) WOCBP must agree to follow instructions for method(s) of contraception for the duration of treatment with study drug plus 5 half-lives of belatacept (50 days) plus 30 days (duration of ovulatory cycle) for a total of 80 days following treatment completion.
- e) Males who are sexually active with WOCBP must agree to follow instructions for method(s) of contraception for the duration of treatment with study drug(s) plus 5 half-lives of the belatacept (50 days) plus 90 days (duration of sperm turnover) for a total of 140 days following treatment completion.
- f) Azoospermic males and WOCBP who are continuously not heterosexually active are exempt from contraceptive requirements. However, WOCBP must still undergo pregnancy testing as described in this section.
- g) Men must be willing to refrain from sperm donation for 140 days after dosing.

Investigators shall counsel WOCBP and male subjects who are sexually active with WOCBP on the importance of pregnancy prevention and the implications of an unexpected pregnancy. Investigators shall advise WOCBP and male subjects who are sexually active with WOCBP on the use of highly effective methods of contraception. Highly effective methods of contraception have a failure rate of < 1% when used consistently and correctly.

At a minimum, subjects must agree to the use of 1 method of highly effective contraception as listed below:

HIGHLY EFFECTIVE METHODS OF CONTRACEPTION

- Male condoms with spermicide
- Hormonal methods of contraception including combined oral contraceptive pills, vaginal ring, injectables, implants and intrauterine devices (IUDs) such as Mirena® by WOCBP

subject or male subject's WOCBP partner. Female partners of male subjects participating in the study may use hormone based contraceptives as one of the acceptable methods of contraception since they will not be receiving study drug

- IUDs, such as ParaGard®
- Tubal ligation
- Vasectomy
- Complete Abstinence*

*Complete abstinence is defined as complete avoidance of heterosexual intercourse and is an acceptable form of contraception for all study drugs. Female subjects must continue to have pregnancy tests. Acceptable alternate methods of highly effective contraception must be discussed in the event that the subject chooses to forego complete abstinence.

3.3.2 Exclusion Criteria

1. Target Disease Exceptions

- a) Subjects with active tuberculosis (TB) requiring treatment; subjects with a history of active or latent TB without documented adequate therapy; subjects with current clinical, radiographic, or laboratory evidence of active or latent TB. All subjects will be required to have a negative QuantiFERON-TB Gold test at the screening visit. A QuantiFERON-TB Gold test performed within 4 weeks of dosing on Day 1 will be acceptable provided there is documentation of a negative result. All subjects will be required to have a negative chest x-ray [posterior-anterior and lateral views] for TB at the screening visit. A chest x-ray performed within the past 6 months will be acceptable provided written documentation of negative results is available.
- b) History of malignancy or strong family history of malignancy.
- c) History of herpes zoster.
- d) Any acute or chronic bacterial infection in the previous 12 weeks.
- e) Any recent infection requiring antibiotic treatment within 4 weeks of dosing.
- f) Known or suspected infection, including infection with human immunodeficiency virus (HIV), hepatitis B or C viruses.
- g) Presence of any factors that would predispose the subject to develop infection (eg, rectal fissures, poor dentition, open skin lesions).
- h) Known or suspected autoimmune disorder.
- i) Any history of known or suspected congenital or acquired immunodeficiency state or condition that would compromise the subject's immune status.

2. Medical History and Concurrent Diseases

- a) Any significant acute or chronic medical illness.
- b) History of clinically relevant hypertension that requires treatment.
- c) Any major surgery within 4 weeks of study drug administration.
- d) Donation of blood to a blood bank or in a clinical study (except a screening or follow-up visit) within 4 weeks of study drug administration (within 2 weeks for plasma only).

- e) Blood transfusion within 4 weeks of study drug administration.
- f) Inability to tolerate IV medication.
- g) Inability to be venipunctured and/or tolerate venous access.
- h) Smoking within less than 6 months of study drug administration.
- i) Recent (within 6 months of study drug administration) drug or alcohol abuse as defined in DSM IV, Diagnostic Criteria for Drug and Alcohol Abuse⁷ ([Appendix 1](#)).
- j) Any other sound medical, psychiatric, and/or social reason as determined by the investigator.

3. Physical and Laboratory Test Findings

- a) Evidence of organ dysfunction or any clinically significant deviation from normal in physical examination, vital signs, ECG or clinical laboratory determinations beyond what is consistent with the target population.
- b) Any of the following on 12-lead ECG prior to study drug administration, confirmed by a repeat test.
 - i) PR \geq 210 msec
 - ii) QRS \geq 120 msec
 - iii) QT \geq 500 msec
 - iv) QT interval corrected with Fridericia's method \geq 450 msec
- c) Screening or Day 1 predose systolic blood pressure $>$ 140 mm Hg or diastolic blood pressure $>$ 90 mm Hg, confirmed by repeat assessment.
- d) Positive urine screen for drugs of abuse.
- e) Positive blood screen for hepatitis C antibody, hepatitis B surface antigen, or HIV-1 or -2 antibody.
- f) Positive urine screen for cotinine.
- g) Positive alcohol screening test.
- h) Any of the following laboratory results outside of the range specified below prior to study drug administration, confirmed by repeat test
 - i) Alanine aminotransferase (ALT) or aspartate aminotransferase (AST) $>$ upper limit of normal (ULN)
 - ii) Total bilirubin $>$ ULN
 - iii) Hemoglobin $<$ 0.9 \times lower limit of normal
 - iv) Creatinine $>$ ULN

4. Allergies and Adverse Drug Reaction

- a) History of allergy to belatacept or related compounds.
- b) History of any significant drug allergy (such as anaphylaxis or hepatotoxicity).

5. Other Exclusion Criteria

- a) Prisoners or subjects who are involuntarily incarcerated.
- b) Subjects who are compulsorily detained for treatment of either a psychiatric or physical (eg, infectious disease) illness.
- c) Inability to comply with restrictions and prohibited activities/treatments as listed in Section 3.4.

Eligibility criteria for this study have been carefully considered to ensure the safety of the study subjects and that the results of the study can be used. It is imperative that subjects fully meet all eligibility criteria.

3.3.3 *Women of Childbearing Potential*

WOCBP is defined as any female who has experienced menarche and who has not undergone surgical sterilization (hysterectomy or bilateral oophorectomy) and is not postmenopausal. Menopause is defined as 12 months of amenorrhea in a woman over age 45 in the absence of other biological or physiological causes. In addition, females under the age of 55 years must have a documented serum follicle-stimulating hormone (FSH) level > 40 mIU/mL to confirm menopause.

Females treated with hormone replacement therapy (HRT) are likely to have artificially suppressed FSH levels and may require a washout period in order to obtain a physiologic FSH level. The duration of the washout period is a function of the type of HRT used. The duration of the washout period below are suggested guidelines and the investigators should use their judgment in checking serum FSH levels. If the serum FSH level is > 40 mIU/mL at any time during the washout period, the woman can be considered postmenopausal.

- 1 week minimum for vaginal hormonal products (eg, rings, creams, gels)
- 4 week minimum for transdermal products
- 8 week minimum for oral products

Other parenteral products may require washout periods as long as 6 months.

3.4 *Concomitant Treatments*

3.4.1 *Prohibited and/or Restricted Treatments*

Prohibited and/or restricted medications taken prior to study drug administration in the study are described below. Medications taken within 4 weeks prior to study drug administration must be recorded on the case report form (CRF).

- 1) Prior exposure to abatacept and/or belatacept or leukocyte-depleting agents (eg, rituximab).
- 2) Exposure to any investigational drug within 4 weeks of study drug administration.
- 3) Use of any prescription drugs within 4 weeks prior to study drug administration except those medications cleared by the PPD medical monitor after consultation with the BMS clinical/medical monitor.
- 4) Use of any other drugs, including over-the-counter medications (OTC) and herbal preparations, including St John's wort, within 1 week or 5 half-lives, whichever is longer, prior to study drug administration except those medications cleared by the PPD medical monitor after consultation with the BMS clinical/medical monitor.

- 5) Administration of oral polio vaccine or live varicella vaccine to subjects or household contacts during the course of the study.
- 6) Vaccination with any live vaccine within the past 4 weeks prior to dosing and for 71 days post dosing.

No concomitant medications (prescription, OTC, or herbal) are to be administered during the study unless they are prescribed by the investigator for treatment of specific clinical events. Any concomitant therapies must be recorded on the CRF.

3.4.2 Other Restrictions and Precautions

- 1) Subjects are to refrain from strenuous exercise, contact sports, and sunbathing for the duration of the study.
- 2) Subjects are not permitted to consume alcohol-containing beverages from 3 days prior to first dose until clinic furlough.
- 3) Subjects are required to remain in the clinical facility at least 72 hours after dosing until furloughed.
- 4) Subjects are required to fast (nothing to eat or drink except water) for 4 hours before until 2 hours after study drug administration.
- 5) On Day 1, all subjects will receive identical meals.
 - A standard light breakfast will be served approximately 2 hours postdose.
 - A standard lunch will be served approximately 4 hours postdose.
 - A standard dinner will be served approximately 8 hours postdose.
 - A standard light snack will be served approximately 12 hours postdose.The food content of meals may vary on Days 2 through 4.
- 6) Subjects should maintain an upright (seated or reclining) position for at least 4 hours postdose on Day 1.

3.5 Discontinuation of Subjects following any Treatment with Study Drug

Subjects MUST discontinue investigational product (and non-investigational product at the discretion of the investigator) for any of the following reasons:

- Subject's request to stop study treatment and/or participation in the study
- Any clinical AE, laboratory abnormality or intercurrent illness which, in the opinion of the investigator, indicates that continued participation in the study is not in the best interest of the subject
- Termination of the study by BMS
- Loss of ability to freely provide consent through imprisonment or involuntarily incarceration for treatment of either a psychiatric or physical (eg, infectious disease) illness
- Unblinding a subject for any reason (emergency or nonemergency)
- Inability to comply with protocol
- Discretion of the investigator
- Pregnancy

In the case of pregnancy, the PPD medical monitor or designee must immediately notify the BMS medical monitor or designee of this event. In most cases, the study drug will be permanently discontinued in an appropriate manner. If the investigator determines a possible

favorable benefit/risk ratio that warrants continuation of study drug, a discussion between the investigator and the BMS Medical Monitor or designee must occur.

All subjects who discontinue the study drug should comply with protocol-specified follow-up procedures as outlined in [Section 5](#). The only exception to this requirement is when a subject withdraws consent for all study procedures including post-treatment study follow-up or loses the ability to consent freely (ie, is imprisoned or involuntarily incarcerated for the treatment of either a psychiatric or physical illness).

If study drug is discontinued prior to the subject's completion of the study, the reason for the discontinuation must be documented in the subject's medical records and entered on the appropriate CRF page.

3.6 Post Study Drug Follow-up

Subjects who discontinue study drug may continue to be followed.

3.6.1 Withdrawal of Consent

Subjects who request to discontinue study drug will remain in the study and must continue to be followed for protocol specified follow-up procedures. The only exception to this is when a subject specifically withdraws consent for any further contact with him/her or persons previously authorized by the subject to provide this information. Subjects should notify the investigator of the decision to withdraw consent from future follow-up **in writing**, whenever possible. The withdrawal of consent should be explained in detail in the medical records by the investigator, as to whether the withdrawal is from further treatment with study drug only or also from study procedures and/or post-treatment study follow-up, and entered on the appropriate CRF page. In the event that vital status (whether the subject is alive or dead) is being measured, publicly available information should be used to determine vital status only as appropriately directed in accordance with local law.

3.6.2 Lost to Follow-up

All reasonable efforts must be made to locate subjects to determine and report their ongoing status. This includes follow-up with persons authorized by the subject as noted above. Lost to follow-up is defined by the inability to reach the subject after a minimum of 3 documented phone calls, faxes, texts, or emails as well as lack of response by subject to 1 registered mail letter. All attempts should be documented in the subject's medical records. If it is determined that the subject has died, the site will use permissible local methods to obtain the date and cause of death.

If investigator's use of third-party representative to assist in the follow-up portion of the study has been included in the subject's informed consent, then the investigator may use a sponsor-retained third-party representative to assist site staff with obtaining subject's contact information or other public vital status data necessary to complete the follow-up portion of the study. The site staff and representative will consult publicly available sources, such as public health registries and databases, in order to obtain updated contact information. If after all attempts, the subject remains lost to follow-up, then the last known alive date as determined by the investigator should be reported and documented in the subject's medical records.

4. STUDY DRUG

Study drug includes both investigational [medicinal] product (IP/IMP) and non-investigational [medicinal] product (Non-IP/Non-IMP) and can consist of the following:

- All products, active or placebo, being tested or used as a comparator in a clinical trial.
- Study required premedication.
- Other drugs administered as part of the study that are critical to claims of efficacy (eg, background therapy, rescue medications).
- Diagnostic agents: (eg, glucose for glucose challenge) given as part of the protocol requirements must also be included in the dosing data collection.

After at least a 4-hour fast, on Day 1 each subject will receive a single 10 mg/kg IV dose of either belatacept Process E or belatacept Process C infused over 30 minutes according to a randomization schedule:

- Treatment A: belatacept 10 mg/kg IV, Process E belatacept
- Treatment B: belatacept 10 mg/kg IV, Process C belatacept

Belatacept process E (Treatment A) or belatacept process C (Treatment B) will be administered intravenously, at a dose of 10 mg/kg using a calibrated, constant-rate infusion pump. The continuous infusion solution must be filtered upon administration using an in-line, sterile, nonpyrogenic, low-protein binding filter with a pore size of 1.2 microns. Belatacept infusion should be administered over a period of 30 minutes, in a fixed volume of 100 mL, using 0.9% sodium chloride (normal saline) as diluent, to produce a final infusion concentration of 2 mg/mL to 10 mg/mL. If normal saline cannot be obtained sites may use 5% dextrose in water as an acceptable alternative.

The time at the start of the infusion will be called “0” hour. The IV infusion of study drug will be administered with the subject in the seated or reclining position. At the end of the infusion, the line must be flushed per the belatacept pharmacy manual for this study. Any unused portion of the infusion solution should not be stored for reuse.

Belatacept infusion must be completed within 24 hours of reconstitution of the lyophilized powder, If not used immediately the infusion solution may be stored under refrigerated conditions: 2°C to 8°C (36°F to 46°F) and protected from light for up to 24 hours (4 of these hours may be at room temperature, 20°C to 25°C [68°F to 77°F], and normal light).

Product description and storage information is described in [Table 4-1](#).

Table 4-1: Study Drugs for IM103349

Product Description Dosage Form	Potency	IP/Non-IMP	Blinded or Open Label	Packaging/Appearance	Storage Conditions (per label)
Belatacept for IV infusion, 250 mg/vial (Process C)	250 mg vial	IP	Open label	White to off white, whole or fragmented cake in a vial.	Store refrigerated, 2°C-8°C (36°F-46°F); Protect from light.
Belatacept for IV infusion, 250 mg/vial (Process E)	250 mg vial	IP	Open label	White to off white, whole or fragmented cake in a vial.	Store refrigerated, 2°C-8°C (36°F-46°F); Protect from light.

Abbreviations: IP=investigational product; IV=intravenous.

4.1 Investigational Product

An investigational product, also known as investigational medicinal product in some regions, is defined as a pharmaceutical form of an active substance or placebo being tested or used as a reference in a clinical study, including products already with a marketing authorization but used or assembled (formulated or packaged) differently than the authorized form, or used for an unauthorized indication, or when used to gain further information about the authorized form.

The investigational product should be stored in a secure area according to local regulations. It is the responsibility of the investigator to ensure that investigational product is only dispensed to study subjects. The investigational product must be dispensed only from official study sites by authorized personnel according to local regulations.

4.2 Non-investigational Product

Other medications used as support or escape medication for preventative, diagnostic, or therapeutic reasons, as components of the standard of care for a given diagnosis, may be considered as non-investigational products.

4.3 Storage and Dispensing

The product storage manager should ensure that the study drug is stored in accordance with the environmental conditions (temperature, light, and humidity) as determined by BMS. If concerns regarding the quality or appearance of the study drug arise, the study drug should not be dispensed and the BMS medical monitor should be contacted immediately.

Study drug not supplied by BMS will be stored in accordance with the package insert. Investigational product documentation (whether supplied by BMS or not) must be maintained that includes all processes required to ensure drug is accurately administered. This includes documentation of drug storage, administration and, as applicable, storage temperatures, reconstitution, and use of required processes (eg, required diluents, administration sets). Specific instructions for preparation, stability and administration of the IP will be provided in a separate document.

4.4 Method of Assigning Subject Identification

Enrolled subjects, including those not dosed, will be assigned sequential subject numbers starting with 00001, (eg, 00001, 00002, 00003.... 00010). Those enrolled subjects meeting inclusion and exclusion criteria will be eligible to be randomized. Randomization numbers will be assigned prior to dosing.

Previous studies indicate that in subjects who take belatacept, there is a trend in higher clearance with increasing body weight.⁴ In this study, the randomization will be stratified by weight categories: 60 to < 70 kg, 70 to < 80 kg, 80 to < 90 kg, and 90 to 100 kg. Within each weight category, subjects will be randomly assigned to Process E belatacept or Process C belatacept in 1:1 ratio. Randomization numbers will be sequential within each weight category, starting with 1001, 2001, 3001, and 4001 for each weight category, respectively.

Subjects will not be replaced if they are discontinued from the study secondary to an AE unless the AE can be determined to be unrelated to treatment. If a subject is replaced after dosing then the replacement subject will be assigned the original subject's number plus 500. The replacement subject will receive the same treatment as the subject being replaced but a new randomization number will be assigned to him or her. For example, Subject 4 would be replaced by Subject 504.

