Investigational Product(s), Dose and Mode of Administration, Duration of Treatment with Investigational Product(s): Each subject will be administered a single dose of Process E belatacept 10 mg/kg intravenous (IV) or Process C belatacept 10 mg/kg IV infused over 30 minutes according to a randomization schedule.

Study Phase: 1

Research Hypothesis: The pharmacokinetics (PK) of belatacept manufactured by Process E (Process E belatacept) and by Process C (Process C belatacept) are comparable in healthy subjects, based on exposure as measured by area under the serum concentration-time curve (AUC) from time zero extrapolated to infinite time (AUC[INF]) and maximum observed serum concentration (Cmax).

Objectives:

Primary:

The primary objective of this study is to compare the PK of Process E belatacept relative to Process C belatacept following a single-dose IV infusion of 10 mg/kg in healthy subjects.

Secondary:

The secondary objectives are as follows:

- To assess the safety of a single-dose IV infusion of 10 mg/kg Process E belatacept and 10 mg/kg Process C belatacept.
- To assess the immunogenicity of Process E belatacept and Process C belatacept.

Study Design: This is an open-label, randomized, parallel-group, single-dose, biocomparability study in healthy subjects. Due to a number of significant deviations that occurred at Site 2, 30 replacement subjects will be dosed. This protocol allows for replacement of subjects at sponsor discretion. The data from the 30 subjects who were enrolled and dosed at Site 2 will not be included in the primary analysis, and the data from the 30 replacement subjects to be dosed will be used for the primary analysis.

The initial plan was to dose approximately 146 subjects (approximately 73 in each cohort) in order to complete a minimum of 67 subjects per cohort. Given the protocol deviations at Site 2, the number of subjects dosed in this study has now increased to approximately 176 in order to ensure adequate sample size for the primary analysis. Subjects will undergo screening evaluations to determine eligibility within 28 days prior to dosing on Day 1. To allow for possible dropouts, an adequate number of subjects will need to meet the inclusion/exclusion criteria at screening so that 73 subjects per arm will be dosed on Day 1.

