3. INVESTIGATIONAL PLAN

3.1 Study Design and Duration

This is an open-label, randomized, parallel-group, single-dose, biocomparability study in healthy subjects. Due to a number of significant deviations that occurred at Site 2, 30 replacement subjects will be dosed. [Section 4.4](#) allows for replacement of subjects at sponsor discretion. The data from the 30 subjects who were enrolled and dosed at Site 2 will not be included in the primary analysis, and the data from the 30 replacement subjects to be dosed will be used for the primary analysis.

The initial plan was to dose approximately 146 subjects (approximately 73 in each cohort) in order to complete a minimum of 67 subjects per cohort. Given the protocol deviations at Site 2, the number of subjects dosed in this study has now increased to approximately 176 in order to ensure adequate sample size for the primary analysis. Subjects will undergo screening evaluations to determine eligibility within 28 days prior to dosing on Day 1. To allow for possible dropouts, an adequate number of subjects will need to meet the inclusion/exclusion criteria at screening so that 73 subjects per arm will be dosed on Day 1.

Subjects will enter the study site on Day -1 and remain confined until completion of the Hour 72 PK sample collection on Day 4. On Day 1, subjects will be randomly assigned within stratified weight categories in a 1:1 ratio to receive either Process E belatacept or Process C belatacept, 10 mg/kg, IV infused over 30 minutes. Subjects will return to the study site for PK blood sample collections after they are furloughed on Day 4 from the study site. Blood samples will be collected through Day 57 (approximately 5-6 half-lives) for PK analysis and through Day 71 (approximately 7-8 half-lives) for assessment of immunogenicity when drug concentrations are low and unlikely to interfere with analysis of anti-drug antibodies.

The PK and immunogenicity blood sample schedule is shown in [Table 5.5.1-1](#). Blood samples for immunogenicity will be obtained prior to dosing and after dosing on Days 15, 29, 43, 57, and 71.

The study design schematic is presented in [Figure 3.1-1](#).

Figure 3.1-1: Study Design Schematic

Days -28 to -1		Day 1	Day 4	Days 5 to 71	Day 71
S, E	R ^a	10 mg/kg IV Process E belatacept OR 10 mg/kg IV Process C belatacept Serial PK sampling	Furlough After Hour 72 PK sample	PK ^b : Days 8, 15, 22, 29, 36, 43, 57 IMG: Days 15, 29, 43, 57, 71	Discharge ^c

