8.4.4 Pharmacokinetic Analyses

A linear fixed effect model with treatment as a fixed effect will be fitted to the log-transformed PK parameters AUC(INF), Cmax, AUC(0-T) for use in estimation of effects and construction of CIs. To assess comparability of Process E belatacept to Process C belatacept, point estimates and the 2-sided 90% CIs for treatment differences on the log scale will be exponentiated to obtain estimates for ratios of geometric means and respective 90% CIs for belatacept AUC(INF), Cmax, and AUC(0-T) on the original scale. A sensitivity analysis comparing the PK between Process E and Process C may be performed by excluding patients who are positive for anti-belatacept antibodies. Biocomparability of Process E belatacept to Process C belatacept will be concluded if the 90% CIs for the ratios of geometric means for belatacept AUC(INF) and Cmax are contained within 80% to 125%.

All individual PK parameters will be listed for each analyte, including exclusions and reasons for exclusion from summaries. Summary statistics will be provided for each PK parameter by treatment, for belatacept. Geometric means and coefficients of variation will be presented for Cmax, AUC(0-T), AUC(INF), CLT, and Vss by treatment group. Medians and ranges will be presented for Tmax by treatment group. Mean and standard deviation will be provided by treatment group for T-HALF.

Plots of individual AUC(INF), Cmax, and AUC(0-T) combined with corresponding geometric means will be provided versus treatment.

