Prior to protocol amendment 02 (dated September 27, 2016), 146 subjects were dosed at 3 clinic sites: 60 at Site 1 (PPD), 30 at Site 2 (SNBL), and 56 at Site 3 (MRA). Audit and monitoring visits revealed major protocol deviations at Site 2 including but not limited to inclusion/exclusion criteria deviations, not providing HIPAA consent at screening visit, incomplete source documentation, failure to obtain laboratory tests within the pre-specified windows, failure to obtain protocol-specified laboratory tests, and incorrect handling of blood samples. Due to the number and significance of these deviations affecting the data of all subjects at Site 2, the 30 dosed subjects were not considered eligible for the analysis of the study endpoints.

Removing the data from the 30 dosed subjects at Site 2 from the analysis without replacing it would result in a total of 116 dosed subjects and under-power the study (approximately 74% power, assuming a true difference of 11%).

The protocol amendment 02 (dated September 27, 2016) was written to replace those 30 dosed subjects at Site 2 with 30 new subjects at Site 1 and Site 3, in order to maintain sufficient power. Randomization of the 30 new subjects was stratified by weight categories in the same way as for the originally planned subjects.

The 30 dosed subjects at Site 2 will not be included in the analysis and 30 replacement subjects dosed at Site 1 and Site 3 will be included in the analysis. A total of 176 subjects will be dosed including the originally planned 146 subjects and the 30 replacement subjects.

In addition, the data from the subjects who were enrolled at Site 2 will only be presented in the listings and be excluded from any summaries or statistical analyses.

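### Were the 30 Site 2 replacements randomised, or did they inherit the treatment of the subjects they replaced?

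*Protocol*

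**What the plan says.** Three places bear on how the 30 replacements got their treatment.

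- **Protocol 4.4** first sets out 1:1 random assignment within four weight categories. It then covers replacement after dosing: "The replacement subject will receive the same treatment as the subject being replaced", although "a new randomization number will be assigned to him or her". The replacement's subject number is the replaced subject's number plus 500.
- **Protocol 3.1** introduces the 30 Site 2 replacements and says that 4.4 "allows for replacement of subjects at sponsor discretion". The synopsis makes the same point without the cross-reference: "This protocol allows for replacement of subjects at sponsor discretion". Section 3.1 then gives a single Day 1 rule: "subjects will be randomly assigned within stratified weight categories in a 1:1 ratio".
- **SAP section 1** says of the new subjects: "Randomization of the 30 new subjects was stratified by weight categories in the same way as for the originally planned subjects". SAP 2.1 repeats the Day 1 rule and plans about 88 dosed per group, made up of 73 original subjects and 15 replacements.

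The primary model has no weight term: "A linear fixed effect model with treatment as a fixed effect will be fitted to the log-transformed PK parameters" (Protocol 8.4.4).

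**The concern.** All the Site 2 subjects had been dosed, so the after-dosing rule in 4.4 covers their replacements on its face, and 3.1 points to that section. A treatment copied from the replaced subject is not a random 1:1 assignment. If 4.4 was followed as written, about a fifth of the primary-analysis subjects had a treatment fixed before entry in an open-label trial, which leaves room for selection. Section 4.4 does not require the replacement to come from the same weight category. It also reports that clearance tends to rise with body weight, and the model would not adjust for a weight imbalance. The SAP says (section 2.4) that it reflects Amendment 02, yet it flags no departure from 4.4. The cross-reference also fails: the published 4.4 contains no sponsor-discretion ground for replacement.

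**Working it through.** **1. The texts side by side**

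| Question | Protocol 4.4 | Protocol 3.1 | SAP 1 and 2.1 |
|---|---|---|---|
| Is it about these 30? | No, general rule | Yes, for permission to replace | Yes |
| How is treatment set? | Copied from replaced subject | Random, 1:1, by weight category | Random, by weight category |
| Tense | Future | Future | Past (SAP 1) |

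Section 3.1 uses 4.4 as authority to replace, not as the method of allocation; the method it states is random assignment. No text says that any of the 30 inherited a treatment. The specific account and the Day 1 rule agree, and only the general rule disagrees.

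The conflict is also narrower than it looks. Under 4.4 each replacement gets a new randomization number, and those numbers run in sequence within weight category, so some handling by weight fits both texts. What remains is random versus inherited treatment.

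**2. Does the choice of rule affect power?**

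Inputs from the synopsis: 90% CI within 0.80 to 1.25 for both endpoints; CV 20% for AUC(INF) and 26% for Cmax; true ratio 1.11 or 0.90; 67 per group.

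Method: two one-sided t-tests on the log scale, with standard deviation √ln(1+CV²), so √ln(1.04) = 0.198 and √ln(1.0676) = 0.256. The standard error is the standard deviation times √(1/n₁+1/n₂). Overall power is the product of the two endpoint powers (independence assumed).

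The plan's own figures first:

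- 67 v 67, ratio 0.90: 0.962 × 0.843 = 81.1% (stated: at least 96%, 84% and 81%).
- 67 v 67, ratio 1.11: 0.965 × 0.848 = 81.9% from unrounded factors.
- 58 v 58 (the 116 without replacements): 75.3% at ratio 1.11 and 74.5% at 0.90. Taking the CV itself as the log-scale standard deviation gives 73.9% at 1.11. SAP section 1 states about 74%.

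The two rules differ in arm sizes. Inheritance restores the original split. Fresh 15:15 allocation leaves a gap if Site 2 was uneven. The documents do not give the Site 2 split, so the following are assumptions:

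- 146 dosed, originally 73:73, no dropout, ratio 1.11. Inherited: 73 v 73, power 85.3%. Fresh, with Site 2 split 10:20: 73 − 10 + 15 = 78 v 73 − 20 + 15 = 68, power 85.1%.
- 134 evaluable, ratio 0.90: 67 v 67 gives 81.1% and 59 v 75 gives 80.5%.

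**3. How far could unmatched weight move the ratio?**

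This arises only if treatments were inherited. Dose is 10 mg/kg, so it rises with weight. If clearance varies as weight^b, AUC varies as weight^(1−b). The documents give no value of b, so take 0 to 1. Assume a large 10 kg difference in mean weight between 15 and 15 replacements, the other subjects balanced, and a mean of 80 kg:

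- Difference between the full arms: 10 × 15/73 = 2.05 kg; weight ratio 82.05/80 = 1.026.
- AUC shift: 0% at b = 1; 1.026^0.5 − 1 = 1.3% at b = 0.5; 2.6% at b = 0.

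A positive trend of clearance with weight means b above 0, hence less than 2.6%, against limits of 0.80 and 1.25.

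**4. Would a departure come to light?**

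SAP 7.4 lists study drug administration and the randomization schedule by subject. SAP 7.2 says that relevant protocol deviations will be documented. If the plus-500 numbering was used, each replacement can be paired with the subject replaced.

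**The case for a change.** The best case for a change is that 4.4 carries no limit to individual dropouts and 3.1 links it expressly to Site 2. A new randomization number does not rescue the reading, because 4.4 sets it against an inherited treatment. The count of 15 per group is not decisive, since inheritance gives the same count if Site 2 was split 15:15. Protocol 9.1.1 requires the study to be conducted as the approved protocol describes, so if the SAP is right, 4.4 was not followed to the letter and neither document says so. Whether a fifth of the subjects were randomised should not be left to inference, and a sentence would settle it.

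Much of this stands as a description of the text. The mismatch is real, the cross-reference is wrong, and neither the new number nor the 15 per group proves anything alone. What does not stand is that a reader cannot tell which rule applied. The SAP speaks about these 30 directly and reports their randomization as done. The failed cross-reference takes nothing away from the authority to replace, which the synopsis states and Amendment 02 exercises by adding the 30.

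The selection risk would be real under inherited treatment, and assay-measured endpoints would not remove it. But it depends on an event that no text reports.

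**Conclusion.** No change to the plan follows. This is a clerical slip: a general replacement rule and a cross-reference were not edited when Amendment 02 added the 30 subjects. An edit would restate what the SAP says was already done, and would leave the allocation, the model, the 0.80 to 1.25 criterion and the conclusion as they are. The effect on power is below one percentage point in the cases examined (85.3% against 85.1%; 81.1% against 80.5%). A supportive analysis without the 30 is not called for, and it would run at about the 74% power that the SAP itself regards as too low.

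This rests on taking the SAP's account of the randomization as accurate. The power comparisons also assume original arms of 73 each or 134 evaluable subjects, with hypothetical splits. The weight illustration rests on an assumed 10 kg difference and an assumed range for b. If the by-subject listings showed that treatments had been inherited, the question would reopen as a deviation to be reported. Nothing in the documents indicates that.
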